**Study Protocol for
Comparison air versus carbon dioxide insufflation in single balloon anterograde enteroscopy**

NCT 03811522

1/11/2019

Significance/Background:

Endoscopy is a valuable tool utilized by gastroenterologist to inspect the length of the gastrointestinal tract. The gastrointestinal tract is a hollow viscous and is contracted in its normal state. In order to expand a contracted portion of the gastrointestinal tract insufflation is required. Two approaches utilized in insufflation are air and carbon dioxide (CO₂). The vast majority of endoscopy utilize air insufflation given it ease and lower cost. It's increase retention in the lumen provides good expansion, however, with prolonged endoscopic procedures side effects from air insufflation can occur symptoms such as abdominal pain, nausea, and bloating/abdominal distention are a result of the retention of air in the lumen.

Carbon dioxide is the alternative to air insufflation. It is commonly used gas utilized in many fields of medicine most commonly in laparoscopic and endoscopic procedures. CO₂ in the GI tract is absorbed about 160 times greater than nitrogen (the major component of insufflated air). Once the CO₂ is absorbed through the mucosa of the GI tract it crosses into the bloodstream and is exhaled through the lungs.^{3,5} This rapid absorption coupled with the potential vasodilatory effect of CO₂ in mucosa seen in animal studies are believed to be the reason behind reduced post procedural distension and pain.^{4,5}

There are 9 randomized controlled studies which have evaluated CO₂ insufflation gas; 6 of them studying colonoscopy and the others involve either sigmoidoscopy, ERCP, and double-balloon endoscopy. All of which find CO₂ to be superior with patients experiencing less pain and bowel distension.³ CO₂ insufflation is considered by many endoscopists to be superior to air insufflation and its use is actually advocated by American Society for Gastrointestinal Endoscopy (ASGE) as the insufflation gas of choice for procedures that carry a high risk of perforation.^{3,6,7,8} Although CO₂ insufflation has its reservations primarily in those patients with predisposed pulmonary conditions due to their reduced ability to expel carbon dioxide, many early studies had even excluded patients with known pulmonology diseases. Crossover trial data and 2 additional studies that evaluated the safety in CO₂ insufflation in patients with diminished pulmonary function showed no significant difference in the rise of ETCO₂, during or after the procedure and adverse events were similar between both patient arms of both studies. THIS NEEDS TO BE BEEFED UP AND WITH CITATIONS

CO₂ insufflation has been demonstrated safe, effective, and capable of reducing patient's post procedural symptoms in multiple studies involving colonoscopy, flexible sigmoidoscopy, ERCP, balloon

assisted enteroscopy and endoscopic submucosal dissection.^{1,2,3,9,10,11} Despite the vast amount of literature on air versus carbon dioxide insufflation there is limited data for single balloon anterograde enteroscopy. Our hypothesis is that anterograde single balloon enteroscopy that utilizes carbon dioxide insufflation will have fewer symptoms of abdominal pain, nausea, and bloating as compared to air insufflation.

Objective(s): Identify if the use of carbon dioxide insufflation can reduce the amount of post-operative pain, nausea, and bloating with single balloon endoscopy.

Primary Outcome Variable(s):

1. Does the use of carbon dioxide for insufflation reduce the amount of postoperative pain compared to air insufflation?

Secondary Outcome Variable(s):

1. Average time of procedure air vs carbon dioxide insufflation.
2. Type and amount of anesthetic used air vs carbon dioxide insufflation

Setting/Resources for the Study:

Patients will be recruited/consented/randomized by the GI fellow and [name]D. during the patient's routine office visit to discuss their pending procedure. This will take place in a private consultation room to ensure privacy and should take approximately 10-15 minutes. In order to minimize coercion, it will be

made very clear to patients that their participation is voluntary, and that participation will in no way affect their future care. Randomization will be performed using a sealed envelope system. All patients are to receive a copy of the informed consent.

Study Procedures:

The single balloon enteroscopy is performed with Olympus (SIF-Q180) and operated by a single experienced endoscopist, [name]D., with over 1,000 single balloon endoscopies have been performed. Additional assistance provided via 3 gastroenterology fellows ([name], [name], and [name]). All anterograde enteroscopy procedures are to be performed in the surgical suite with general anesthesia. Patient CO₂ levels will be noninvasively monitored by anesthesia with End-Tidal Carbon Dioxide (ETCO₂). Anesthesia will be administered at the discretion of the consulting anesthesiologist via fentanyl, versed, and propofol. Insufflation utilized during procedure determined via randomization to air or carbon dioxide prior to procedure. The rate of air or carbon dioxide (level) is left to discretion of acting endoscopists for proper insufflation of bowel to achieve adequate luminal views. CO₂ insufflator to be used is a Stratus CO₂ insufflator made by Medivators.

After completion of procedure determination of patient pain level will be assessed at 15 minutes, 30 minutes, and 1-hour and 24-hour intervals using a patient survey. Pain is assessed based on the horizontal assessment scale (HAS). This scale based on a horizontal line measuring 100mm in length. Patient will be asked at the afore mentioned time intervals to mark with pen their level of pain on the HAS. The mark will then be measured in millimeters to determine score of pain. Score will be in a range from 0 to 100mm. Zero being no pain at all and 100mm the maximum pain level. The HAS is then documented with type of insufflation utilized and time interval. Patient will also be asked about nausea, abdominal fullness, and bloating after procedure to be ranked on a 0 to 10 scale, with zero being nothing to 10 as severe. This will also be ascertained at 15 minutes, 30 minutes, 1 hours and 24 hours. The 24 hours assessment for pain as well as dyspepsia symptoms is achieved through patients receiving HAS scale along with a questionnaire asking to rank dyspeptic symptoms. The HAS scale and dyspeptic questionnaire will be marked with patient identification number. A self-address envelope with postage will be given to patient with instruction return once completed within 24 hours of original procedure. Instruction sheets along with how to take dyspeptic survey will also be given.

Data collected from the chart will include patient demographics, operative technique, complications.

Standard of care follow-up will occur at the outpatient office with [name]D. and GI fellow.

Early Withdrawal of Subjects:

A patient may withdraw at any time from the study and data that had already been collected on these patients will still be used.

Sample Size Determination:

The primary outcome variable is improved patient pain, bloating, abdominal fullness, and nausea. Previous studies show varied sample sizes, from 40 total patients to 300. Our goal is 25-40 persons in each procedure group, for a total of 50-80 patients.

Statistical Methods:

Data will be entered into Microsoft Excel 2017 and SPSS version 22 statistical programs. Analysis will include descriptive statistics, t-test, standard error, Pearson and fisher exact test. Statistical significance will be established with α of 0.05 for all comparisons.

Potential Benefits:

While nothing can be guaranteed, the hypothesis is that patients in the CO2 insufflation group may experience less pain, bloating, and nausea. The patients may not benefit from their participation in this study.

Adverse Events:

Risks consist of those entailed with general anesthesia and single balloon endoscopy. The risk of CO2 insufflation consists of respiratory depression and CO2 embolism.¹⁶

Recording of Adverse Events:

At each contact with the subject, the investigator will seek information on adverse events by specific questioning and, as appropriate, by examination. Information on all adverse events will be recorded immediately (e.g., signs, symptoms, abnormal diagnostic procedures). The clinical course of each event will be followed until resolution, stabilization, or until it has been determined that the study treatment or participation is not the cause.

Reporting of Serious Adverse Events

Reports of all serious adverse events (including follow-up information) will be submitted to the St. Elizabeth's Mercy Health IRB within five business days.

Data Management and Confidentiality

Patient data will be entered into electronic spreadsheets. The spreadsheet will be stored as separate file, protected by unique passwords. Only the investigators will have access to the files and their passwords. Paper records will be stored in hard copy in a locked filing cabinet in the investigator's office or at the hospital's endoscopy suit. Should any new significant findings be made during the study, the patient will be made privy to these findings in a timely manner.

Provisions to Protect the Privacy Interests of Subjects

Patient consent and all other research related activities will take place in a private exam room. Patient will also be receiving a copy of their informed consent.

Funding Source:

No funding is being sought for this study or being received.

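### The hypothesis is about abdominal pain, but the protocol names no body site for the primary pain score, so pain unrelated to the gas can enter it and cost power

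*Combined protocol and SAP*

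**What the plan says.** **Target symptom.** Significance/Background gives the mechanism: "symptoms such as abdominal pain, nausea, and bloating/abdominal distention are a result of the retention of air in the lumen". Its closing hypothesis is that patients given CO₂ "will have fewer symptoms of abdominal pain, nausea, and bloating as compared to air insufflation".

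**Primary outcome.** Primary Outcome 1 names no site: "Does the use of carbon dioxide for insufflation reduce the amount of postoperative pain compared to air insufflation". Objective(s) also refers to pain without a site.

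**Instrument.** In Study Procedures the patient is to "mark with pen their level of pain on the HAS" (the HAS is the 100 mm horizontal line), with anchors "Zero being no pain at all and 100mm the maximum pain level". The timing is: "After completion of procedure determination of patient pain level will be assessed at 15 minutes, 30 minutes, and 1-hour and 24-hour intervals". All four scores come after the procedure.

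**Other symptoms.** The same section does name a site for one item: "Patient will also be asked about nausea, abdominal fullness, and bloating after procedure to be ranked on a 0 to 10 scale".

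**Related safeguards.** Study Subjects excludes people with more than 3 months of analgesic use in the past 6 months. The protocol describes no pre-procedure pain score and no item for pain elsewhere, and Statistical Methods lists a t-test without covariates.

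**The concern.** The mechanism can act only on pain that comes from gas in the bowel. A patient who follows the instruction literally may mark pain from any site. Study Procedures states: "All anterograde enteroscopy procedures are to be performed in the surgical suite with general anesthesia". With an oral scope and general anesthesia, a sore throat is a plausible inference in either arm, and so is long-standing back or joint pain in someone who does not take long-term analgesics. A patient with no abdominal pain and a 40 mm sore throat could then score 40 mm on the primary outcome.

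What is at stake is sensitivity. The protocol calculates that about 350 patients are needed and aims for 50–80, so there is little power to spare. Its stated value is as input to later studies, and a score of unspecified pain is harder to pool or interpret as evidence on gas-related pain.

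**Working it through.** **1. The plan's own figure.** Setting/Resources gives about 350 patients but no power, effect size or SD, so it cannot be reproduced. Back-solving for 175 per arm (two-sided α 0.05, 80% power, both assumed): d = (1.960 + 0.842) × √(2/175) = 0.30. Power is Φ(d√(n/2) − 1.960), which at d = 0.30 gives 0.18 with 25 per arm and 0.27 with 40.

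**2. Other pain that adds.** If independent other pain has an SD of r times the abdominal-pain SD, the raw difference is unchanged and d becomes d/√(1 + r²). The sample needed grows by 1 + r². From 350, r = 0.5 gives 350 × 1.25 ≈ 438, and r = 1 gives 350 × 2 = 700.

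**3. Illustration in millimetres.** Every input here is an assumption:
- Abdominal pain is normal, 30 mm (air) vs 20 mm (CO₂), SD 20, clipped to 0–100. After clipping, the difference is 8.9 mm, the SD 18.1 and d 0.49. Power is 0.41 with 25 per arm and 0.60 with 40.
- A fraction p of patients in both arms also has other pain with mean m and SD 15.
- The patient marks either the worse of the two pains or their sum (capped at 100 mm).
- Inflation = (d without other pain ÷ d with it)².

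I simulated 3 million patients per arm:

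| p, m | Worst pain: difference / SD = d | Inflation | Power, 40 per arm | Sum: difference / SD = d | Inflation | Power, 40 per arm |
|---|---|---|---|---|---|---|
| 5%, 10 mm | 8.83 / 18.03 = 0.490 | 1.01 | 0.59 | 8.92 / 18.48 = 0.483 | 1.04 | 0.58 |
| 10%, 30 mm | 8.46 / 18.12 = 0.467 | 1.11 | 0.55 | 8.91 / 20.62 = 0.432 | 1.30 | 0.49 |
| 20%, 20 mm | 8.29 / 17.77 = 0.467 | 1.12 | 0.55 | 8.89 / 20.74 = 0.429 | 1.32 | 0.48 |
| 30%, 30 mm | 7.51 / 17.90 = 0.419 | 1.38 | 0.47 | 8.82 / 23.80 = 0.371 | 1.77 | 0.38 |
| 50%, 40 mm | 5.86 / 18.62 = 0.315 | 2.45 | 0.29 | 8.55 / 27.90 = 0.307 | 2.58 | 0.28 |

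**4. Hand check (30%, 30 mm, sum).** The variance of other pain is 0.3 × (15² + 30²) − (0.3 × 30)² = 337.5 − 81 = 256.5. The inflation is 1 + 256.5/18.1² = 1 + 256.5/327.6 = 1.78. The simulation gives 1.77; the scale limits explain the small gap.

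**5. Reading.** Power falls under both ways of marking, by different routes. When pains add, the raw difference is 96–100% preserved and the SD rises. When the worst pain is marked, the SD hardly moves and the raw difference falls, by 1–5% in the first two rows and by 7–34% in the last three.

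**The case against.** **The instrument matches the stated outcome.** The objective, Primary Outcome 1, Sample Size Determination and Potential Benefits all speak of pain without a site, and total pain after a procedure is a legitimate patient-centred outcome. This stands. The gap is between the hypothesis with its mechanism and the outcome with its instrument, and the sponsor should say which is meant.

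**The patient form is not in the documents.** It may already say abdominal pain, and nearby items on fullness and bloating may steer patients to the abdomen. This also stands. A reader might infer that the trial has no abdominal pain score. The documents show only that the protocol specifies no site.

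**Randomization balances other pain.** It does, so no false benefit arises. A reader might infer that the difference must be pulled towards zero, but material shrinkage of the raw difference needs worst-pain marking, which the documents do not describe. Balance does not remove the loss of power.

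**The sources of other pain are inferred.** The documents never mention throat or airway pain. Study Subjects also admits retrograde cases, where throat pain from the scope would not apply, and the analgesic exclusion removes some chronic pain. These points limit the likely size; they do not supply the missing site.

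**A null result would be weak anyway.** With 25–40 per arm and d = 0.49, power is only 0.41–0.60 with no other pain at all. So a null result could not be put down to sore throat in particular.

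**Conclusion.** The concern holds as a mismatch of wording with a cost in power. As the protocol is written, pain that the gas cannot affect can enter the primary score, and nothing else in the plan takes it out.

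The size cannot be fixed from the documents. On the assumed values above, the equivalent sample inflation runs from about 1.0 (mild other pain in 5–10% of patients) to about 2.5 (half of patients affected at mean 40 mm). The upper end needs other pain that is worse on average than the abdominal pain assumed in either arm, so it is an outer case.

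A reader might go further and say that the hypothesis as worded is not tested. The documents do not support that: a score that includes abdominal pain tests the hypothesis less sensitively. This is a cheap improvement to the plan and does not invalidate the comparison.

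**What to change.** - In Primary Outcome 1, state abdominal pain.
- In the pain-line instruction at 15 minutes, 30 minutes, 1 hour and 24 hours, ask for abdominal pain, with anchors 0 mm = no abdominal pain and 100 mm = worst abdominal pain.
- Add a tick box for pain elsewhere (throat, other), recorded separately and kept out of the score.
- If the patient form already asks for abdominal pain, leave it and align the protocol text to it.

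**Cost.** A wording change to the form and protocol before use, plus one tick box; no added visits, staff or patients. The trade-off is that the primary score no longer captures total postoperative pain. A sponsor who wants total pain as the primary outcome should say so and word the hypothesis to match.

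### No masking of the patient or of the people handling the self-marked pain sheets is described, although randomisation is placed at the office visit before the procedure

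*Combined protocol and SAP*

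**What the plan says.** Subject Recruitment/Screening/Consent states: "Patients will be recruited/consented/randomized by the GI fellow and" a physician whose name is removed from the file, at the office visit where the coming procedure is discussed. It continues: "This will take place in a private consultation room to ensure privacy and should take approximately 10-15 minutes". On method it says only: "Randomization will be performed using a sealed envelope system". Study Procedures adds that the gas is settled by randomisation before the procedure. It does not say when the envelope is opened, or in whose presence.

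The primary outcome is postoperative pain. Study Procedures has it recorded at 15 minutes, 30 minutes, 1 hour and 24 hours: "Patient will be asked at the afore mentioned time intervals to mark with pen their level of pain on the HAS". The mark is then measured in millimetres by a person who is not identified. After that: "The HAS is then documented with type of insufflation utilized and time interval". In describing the 24-hour mail-back, the same section says: "The HAS scale and dyspeptic questionnaire will be marked with patient identification number". Nausea, fullness and bloating are rated by the patient at the same four times.

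Potential Benefits gives the direction expected: "the hypothesis is that patients in the CO2 insufflation group may experience less pain, bloating, and nausea".

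No section of the available text mentions blinding or masking of anyone.

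**The concern.** A pain mark on a line is a judgement by the patient. It can move if the patient knows which gas was used, or if the person presenting the sheet knows and conveys it. Here three things coincide: a subjective primary outcome, a published expectation in one direction, and an allocation step placed at a visit where the patient is awake. If the arm becomes known, the planned t-test estimates the gas effect plus any reporting shift, and nothing in the data separates the two. A shift towards CO2 would look like confirmation of the hypothesis. More patients would not cure it, because the bias stays the same size while the standard error shrinks.

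**Working it through.** **Reading the text.** Each element that could act as masking was checked in turn.

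- *Sealed envelopes.* These conceal the next assignment before it is made. They do not keep the arm from the patient once the envelope is open.
- *General anesthesia.* The patient cannot see the gas in use. That does not hide an arm revealed at an earlier office visit.
- *Patient identification number on the forms.* This would allow the score to be kept apart from the arm, but no rule says that it is.
- *Order of recording.* The patient marks, the mark is measured, and the gas is then documented. For a single sheet, the score exists before the gas is written beside it. The same patient is scored four times, however. If the 15-minute score is filed with the gas as it is taken, the 30-minute and 1-hour sheets may be handled by someone who has just recorded the gas.

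So none of these elements is set up to mask the patient or the score handler.

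**Illustration of size.** The plan has no figure of its own on this point to reproduce.

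- From the documents: 25 to 40 per group (Sample Size Determination); t-test and alpha 0.05 (Statistical Methods).
- Assumed: two-sided test, one time-point comparison, no true effect, SD of 20, 25 or 30 mm, and an average reporting shift b of 5 mm or 1 mm favouring CO2.

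Formulas: SE = SD × √(2/n) and noncentrality λ = b/SE. The rejection rate is P(|T| > t₀.₉₇₅) for a noncentral t with 2n − 2 degrees of freedom. The critical value is 2.011 at n = 25 (48 df) and 1.991 at n = 40 (78 df).

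Example: n = 25, SD 20, b = 5 gives SE = 20 × √(2/25) = 5.66 mm, λ = 5/5.66 = 0.884 and a rejection rate of 13.9%.

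| n per arm | SD (mm) | SE (mm) | λ at b = 5 | False positives, b = 5 mm |
|---|---|---|---|---|
| 25 | 20 | 5.66 | 0.884 | 13.9% |
| 25 | 25 | 7.07 | 0.707 | 10.7% |
| 25 | 30 | 8.49 | 0.589 | 8.9% |
| 40 | 20 | 4.47 | 1.118 | 19.7% |
| 40 | 25 | 5.59 | 0.894 | 14.3% |
| 40 | 30 | 6.71 | 0.745 | 11.4% |

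With b = 1 mm, the rate lies between 5.2% and 5.6% over all six rows. With b = 0 it is 5.0%.

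**The case against.** The strongest reply is that the documents never say patients are unmasked, and that is right. A reader might infer that patients are told their gas at the office visit. The text does not say so, and an envelope allotted at the visit but opened later, before the procedure, would fit the wording. The remark about the consultation room may refer only to the consent talk. Consent pages were removed from the file and might mention masking. What survives is narrower: the procedures that staff would follow contain no step that prevents disclosure.

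Three other inferences go too far.

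- The sentence that documents the HAS with the gas might be read as showing that the collector knew the arm when the mark was made. It does not. Recording comes after measurement, and every comparative trial must link score and arm somewhere.
- The privacy section says: "Patient consent and all other research related activities will take place in a private exam room". This might seem to place allocation in front of the patient. It cannot be literal, because the procedure takes place in the surgical suite and the 24-hour form comes back by post. It says nothing about disclosure of the arm.
- One might scale the assumed shift against the roughly 350 patients mentioned under Setting/Resources. The protocol gives no endpoint, SD, effect or power behind that number, so the comparison has no documented basis.

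It is also fair to object that the false-positive rates rest wholly on assumptions, and that a very small shift does almost nothing. Both stand.

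**Conclusion.** The concern holds in this form: for a self-marked primary outcome with a stated expectation favouring CO2, nothing in the available procedures keeps the gas from the patient or from those who handle the pain sheets, and randomisation is written into a visit before the procedure. It is an omission in the conduct of the trial that is easily closed. It is not evidence that patients or collectors were in fact unmasked.

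The size is unknown. If the shift were 5 mm and the SD 20-30 mm, the nominal 5% error rate would become about 9-14% at 25 per arm and 11-20% at 40 per arm. At 1 mm it would barely move (5.2-5.6%). These figures show sensitivity and are not estimates. The finding does not depend on them. It rates as a cheap improvement.

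**What to change.** 1. Keep consent at the office visit, and change the wording in Subject Recruitment/Screening/Consent so that randomisation does not happen there.
2. Open the next sequentially numbered opaque envelope in the procedure room, after induction of the general anesthesia already planned.
3. Do not disclose the gas to the patient until the 24-hour form is completed, except where needed to manage or assess an adverse event. Record each disclosure.
4. Label every HAS and symptom sheet with patient ID and time point only. Link the arm at analysis, and reword the sentence in Study Procedures that documents the HAS with the gas.
5. Where existing staff allow, have someone who was not in the procedure room hand over, collect and measure the sheets.
6. Reconcile the anesthesia wording so that step 2 covers every randomised patient. Study Subjects speaks of general anesthesia for the patient without distinction and admits retrograde indications, whereas Study Procedures states it for anterograde procedures.

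The cost is protocol and consent wording, both gas sources ready for each case, and a short staff instruction, which is some effort in an unfunded study. Limits remain: the operator stays unmasked, and some patients may guess their gas or be unmasked for an adverse event.

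### The primary outcome is defined two ways, pain alone or four symptoms, with no primary time point, summary or decision rule

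*Combined protocol and SAP*

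**What the plan says.** - **Primary Outcome Variable(s)** lists one item, pain: "Does the use of carbon dioxide for insufflation reduce the amount of postoperative pain compared to air insufflation".
- **Sample Size Determination** names four symptoms: "The primary outcome variable is improved patient pain, bloating, abdominal fullness, and nausea".
- **Objective(s)** and the hypothesis that closes the background name three: pain, nausea and bloating. Potential Benefits repeats those three.
- **Secondary Outcome Variable(s)** has two entries: "Average time of procedure air vs carbon dioxide insufflation" and "Type and amount of anesthetic used air vs carbon dioxide insufflation". No symptom appears there.
- **Study Procedures** gives the pain schedule, "patient pain level will be assessed at 15 minutes, 30 minutes, and 1-hour and 24-hour intervals", and the pain scale, "Score will be in a range from 0 to 100mm". For the other three symptoms it says "Patient will also be asked about nausea, abdominal fullness, and bloating after procedure to be ranked on a 0 to 10 scale" and "This will also be ascertained at 15 minutes, 30 minutes, 1 hours and 24 hours".
- **Statistical Methods** lists descriptive statistics, the t-test, standard error, Pearson and Fisher's exact test. It ties none of them to an outcome or time, and it sets significance at 0.05 for every comparison.

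**The concern.** A reader cannot tell which result would support the claim that CO2 reduces symptoms. Bloating, abdominal fullness and nausea are primary in one section and appear in neither outcome list in the other. Choosing between the two definitions would not settle it, because pain alone is still measured four times and no time or summary is singled out. A composite of four symptoms would also need a scaling rule, since pain runs to 100 and the other scores to 10, and none is given.

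The missing any/all rule decides how the error rate behaves. If one favourable comparison is enough, the false-positive rate of the claim is well above 5%. If all four symptoms must improve, it is well below. Later studies would inherit whichever symptom and time were chosen once the data had been seen.

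**Working it through.** **Plan's own figure.** The plan states no error rate for the primary claim. Its one calculated number, about 350 patients under Setting/Resources, cannot be reproduced because effect size, SD, power and outcome are not given. Taken as 175 per arm at two-sided 0.05 and an assumed 80% power, it implies a standardised difference of √(2/175) × (1.960 + 0.842) ≈ 0.30. The documents do not say for which outcome.

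**Count of single-time, between-group comparisons.**
- Pain only: 1 × 4 times = 4.
- Three symptoms, as in the objective: 3 × 4 = 12.
- Four symptoms: 4 × 4 = 16.

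The plan does not say that 16 tests will be run. Nor is 16 a ceiling: summaries, composites or dichotomised scores would add further choices.

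**Error rate if any one comparison suffices.** With independent tests it is 1 − 0.95^k, which is 1 − 0.95⁴ = 18.5% for 4 and 1 − 0.95¹⁶ = 56.0% for 16. Symptom scores are likely to be positively correlated, so these are upper-end values.

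**Simulation with correlated scores.** Assumptions: no true effect, normal scores, pooled t-test at two-sided 0.05 (the plan does not state sidedness), and 32 per arm, which lies within the planned 25 to 40. There were 100,000 trials per setting. The documents give no correlations, so one common correlation r among all 16 scores was varied. Results in %:

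| r | any of 16 | pain at any of 4 times | four-symptom composite at any of 4 times | all four favour CO2, one named time | all four favour CO2, each at any time |
|---|---|---|---|---|---|
| 0.3 | 47.9 | 17.6 | 14.2 | 0.01 | 0.5 |
| 0.5 | 37.6 | 15.6 | 11.4 | 0.07 | 1.2 |
| 0.7 | 26.9 | 13.2 | 9.5 | 0.3 | 2.1 |
| 0.9 | 14.7 | 9.4 | 7.3 | 0.9 | 2.7 |

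The nominal level is 5% for the first three result columns and 2.5% for the last two, which count one direction only. The value r = 0.3 is a deliberately low extreme.

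**Sensitivity.**
- If symptom and time correlations multiply, with each set to 0.3, 0.5 or 0.9, any of 16 gives 51.4%, 43.0% or 16.8%. The composite at any time gives 17.7%, 15.6% or 9.3%. All four favouring CO2, each at any time, gives about 0.1% to 2.0%.
- With 25 or 40 per arm, any of 16 and pain at four times move by less than 1 percentage point. At r = 0.3, for example, any of 16 is 48.2% and 47.8%.

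**One test.** Pain at one named time, the mean of the four pain scores, or a composite at one named time, each tested once, gives 4.9% to 5.1%.

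**The case against.** The strongest reply is that the study is exploratory in all but name. Setting/Resources concedes that 350 patients are unlikely to be reached and offers the results as input to later work. That lowers the weight of the error rates. It does not remove the contradiction: the protocol still randomises, states a directional hypothesis, declares a primary outcome and sets a significance threshold.

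A second reply is that the inflation depends on inputs the plan does not contain, namely the correlations and an any-one-suffices rule. That is correct, and the highest figures need the low correlation of 0.3. The simulated rates show scale only; the defect is visible from the text.

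Third, nausea and bloating do have a role in the objective and hypothesis, so only abdominal fullness is wholly absent from the outcomes section and the text around it. This is also fair. But an objective is not an outcome definition, and its three symptoms match neither the one-item list nor the four-symptom statement.

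Finally, an amendment dated before the data are examined may be hard to achieve. Each pain score is recorded together with the gas used, and the investigators hold the files. That is a practical limit on the remedy and does not answer the finding.

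**Conclusion.** The concern holds and must be fixed. Two current sections define the primary outcome incompatibly, and nothing elsewhere resolves which governs, at what time, or by what rule. This conclusion rests on the text alone.

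If any one comparison counts, the false-positive rate is about 9% to 18% on the pain-only definition and 15% to 48% on the four-symptom definition (17% to 51% if correlations multiply). These figures assume correlations of 0.3 to 0.9, two-sided tests and no true effect. If all four symptoms must favour CO2, the rate is at most about 2.7% against 2.5%, so there is no material inflation. That the same plan permits both results is the measure of the problem.

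**What to change.** Before any outcome data are examined:

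1. Make Sample Size Determination agree with Primary Outcome Variable(s): pain on the 100 mm scale.
2. Name one primary pain value per patient, either a single time point or one pre-specified summary of the sponsor's choice, and test it once at two-sided 0.05.
3. List bloating, abdominal fullness, nausea and the remaining pain scores as secondary. Test them in a fixed order or with Holm's method, or report estimates with 95% confidence intervals and no significance claim.
4. Reword the blanket 0.05 rule in Statistical Methods to match.

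The broader objective and hypothesis can stay once the other symptoms are listed as secondary. If the sponsor prefers four primary symptoms, Primary Outcome Variable(s) must say so. It must also give the time point, the any/all or composite rule (with scaling), and the multiplicity control.

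The cost is protocol wording and no new data. The downside is that secondary symptoms and times can no longer each support a stand-alone claim at 0.05. If outcome data by arm have already been seen, the choice should be dated and reported as post hoc.
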